Secondary Outcomes. (a) **Communication with Providers** will be measured with a validated 15-item measure.¹⁰⁸ Participants rate providers from poor to excellent with a sample item as "Treated me with respect." Communication with caregivers will be measured through several dyadic-based measures. (b) **Satisfaction with care** will be measured with 3 reliable items used by [name] in her prior work.¹⁰⁹ Finally, (c) **Adherence to guideline-concurrent follow-up care** will be based on following care guidelines of the American Society of Clinical Oncology¹¹⁰ and measured using self-report items as done in prior work.¹¹¹

Dyadic Factors. (a) **Dyadic support** will be measured with the 5-item scale by Northouse^{112,113} which assesses the perceived support received by each member of the patient-caregiver dyad. (b) **Dyadic perspective**, meaning considering another's point of view about a specific topic like breast cancer, will be assessed with a modified version of the Thinking Beyond Oneself scale.¹¹⁴ This scale has been used in dyadic cancer control research.⁶³ (c) **Social constraints** will be measured with the 5-item Social Constraints Scale.^{115,116} We have used a Spanish translation of this scale and obtained good internal consistency.²

Process Variables. (a) **Satisfaction.** We will assess satisfaction with PCI and UC. (b) **Intervention fidelity.** We will measure adherence to intervention protocols, participants' engagement (attendance, participation), exposure to intervention content, quality of intervention delivery and differentiation between PCI and UC arms.^{117,118} Staff will complete session contact logs and evaluation forms.¹¹⁸

C.2. Analytic Methods

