mediation effects at 6-months.¹¹⁹ We will use linear regression models to estimate the coefficients relating each mediating variable (self-efficacy, social support, and distress) to QOL at 6-months, and also the coefficients relating the intervention to each mediating variable. We will calculate the mediated effects as the products of corresponding coefficients and we will construct 95% confidence intervals according to the methods described by MacKinnon et al.¹¹⁹ With 50 subjects per arm we will have 80% power to detect mediation effects of moderate size (with coefficient parameters of 0.39 or more) for each mediator.¹¹⁹

Aim 3. To evaluate the impact of the PCI intervention on Latina survivors' satisfaction with their cancer care. **H₃:** Survivors in PCI will report greater satisfaction with their cancer care compared to UC participants. With 50 Latina survivors per arm we will have 96% power to detect a clinically significant difference in satisfaction with care of 8 points (0.75 SD given estimated SD of 12)¹²⁰ at a significance level of 0.05. We will use a mixed effects model to compare the two arms with respect to satisfaction with care immediately post intervention and at 6-months, adjusting for statistically significant (at the 0.10 level) predictors of satisfaction with care identified in bivariate analyses. We will again explore whether the effect of the intervention on satisfaction with care is different for sub-groups of participants (e.g., whether the impact of PCI on satisfaction with care differs by geographic region (e.g., NY,CA) or region of origin (e.g., Central America, South American)).

Exploratory Aim: To explore the impact of the PCI intervention on Latina survivors' adherence to guideline-concurrent care and surveillance. Given the exploratory nature of this aim no formal power calculation was performed. We will use logistic regression models to compare the two arms with respect to the binary outcomes of adherence to guideline-concurrent care (hormonal therapy; chemotherapy) and surveillance (mammogram within 12 months), controlling for the statistically significant (at the 0.05 level) covariates identified in bivariate analyses. We will also perform "per protocol" analyses of completers vs. non-completers similar to those described in Aim 1.

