1. Study population, including expected demographics (age, ethnicity, country of origin, gender, stage of disease, time since diagnosis). We will clearly define study eligibility and exclusion criteria.
2. Primary and secondary hypotheses to be tested. We anticipate the overall study aims and hypotheses will remain the same, although we are open to feedback and revisions based on our initial team meeting.
3. Sources and methods of measuring intervention and usual care exposure. We will describe how we will track intervention attendance and uptake of services through usual care. Study team members will use a central study database so that participant tracking is consistent across study sites.
4. Outcomes and co-variables to be tested. We have developed a draft of our baseline assessment measure that includes most (although not all) items we propose to measure, including our primary outcome of QOL. We will provide the study survey in print form and/or provide access to the PROMIS Assessment Center study specific website. We will create data codebooks and clearly indicate how all data is labeled and coded.
5. Coding instructions for all study variables will be provided.
6. Qualitative interview guide. We have included a draft of our interview guide in the appendix. We will provide the final and complete interview guide.
7. Analysis plan. We will create a written document of our planned analyses. This plan will also highlight the roles and contributions of each study team member to expected study deliverables.

We will register our RCT at www.Clinicaltrials.gov prior to enrollment in the RCT.

Although not required (given a budget less than \$500,000 in direct costs per project year), we will be prepared to share study data following the approval of a Data Sharing Plan by all study team members. Below we provide a draft of this plan.

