Appendix D: Draft Baseline Interview

INSTRUCTIONS READ BY RESEARCH ASSISTANT: This questionnaire is for Latina Breast Cancer survivors and their caregivers. Remember that you can skip any question you do not want to answer. We will not have your name or information with your responses. There are no right or wrong answers. Thank you.

SECTION A: BREAST CANCER MEDICAL QUESTIONS – Survivors Only

When you were diagnosed with breast cancer, and where did you live at the time of diagnosis?

Date _____ / _____ State and Country _____
 Month / Year

How old were you when you were diagnosed? _____ years

Please choose one response, indicating, Yes or No.

Was your cancer bilateral (in both breasts)?	Yes	No	Unsure	N/A
Do you remember the grade or stage of your cancer when it was diagnosed? (Grade 0, 1, 2, 3, 4 / Stage 0, I, II, III, IV) If Yes, what grade or stage was the cancer at the time of diagnosis ? _____	Yes	No	Unsure	N/A
Did your cancer spread to your lymph nodes?	Yes	No	Unsure	N/A
Do you remember the size of your tumor? If Yes, what was the size of your tumor? _____	Yes	No	Unsure	N/A
Have you ever been diagnosed with breast cancer a second time? If Yes, how old were you at your 2 nd diagnosis? _____ years Was this a recurrence of the original cancer or a new primary diagnosis? _____ Recurrence _____ New Primary _____ Don't know	Yes	No	Unsure	N/A
Have you had any other type of cancer? If Yes, please specify: _____	Yes	No	Unsure	N/A
Did you have radiation therapy for your breast cancer?	Yes	No	Unsure	N/A
Are you still receiving radiotherapy?	Yes	No	Unsure	N/A
Did you have chemotherapy for your breast cancer?	Yes	No	Unsure	N/A
Are you still receiving chemotherapy?	Yes	No	Unsure	N/A
Did you take any hormone treatment for your breast cancer (For example, Tamoxifen, Femara, Arimidex or Aromasin)? If Yes, for how long? _____ (months / years) If Yes, are you currently taking a hormone? _____ Yes _____ No Which one? _____ For how long? _____ (months / years)	Yes	No	Unsure	N/A

PRINCIPAL INVESTIGATOR (LAST, FIRST, MIDDLE): [name]

Had you had surgery to treat your breast cancer?	Yes	No	Unsure	N/A
Which type of surgery have you had?  Mastectomy  Bilateral Mastectomy  Lumpectomy				

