People of my ethnic group receive the same medical care from doctors and health care workers as people from other groups	Strongly Disagree	Disagree	Neutral	Agree	Strongly Agree	Unsure	Prefer not to answer
Doctors and health care workers do not take the medical complaints of people of my ethnic group seriously	Strongly Disagree	Disagree	Neutral	Agree	Strongly Agree	Unsure	Prefer not to answer
I have personally been treated poorly or unfairly by doctors or health care workers because of my ethnicity	Strongly Disagree	Disagree	Neutral	Agree	Strongly Agree	Unsure	Prefer not to answer
If you don’t speak English fluently you will not receive the same type of care that the people who speaks English well	Strongly Disagree	Disagree	Neutral	Agree	Strongly Agree	Unsure	Prefer not to answer

SECTION M: MEDICAL CARE EXPERIENCES – Survivors and Caregivers

In this section, we list some more things people said about medical care. I'd like to remind you that all of your answers are confidential and there are no right or wrong answers to any questions. We are interested in your opinion. We are interested in how good or bad you feel about the overall medical care you have received from the doctor you see the most often. For caregivers: If you have not received care recently, think about what you would expect if you needed care today. Please indicate how strongly you agree or disagree with each of the following statements. Please choose only one response option for each question.

Doctors are good about explaining the reasons for medical tests	Strongly Disagree	Disagree	Uncertain	Agree	Strongly Agree
I think my doctor's office has everything needed to provide complete medical care.	Strongly Disagree	Disagree	Uncertain	Agree	Strongly Agree
The medical care I have been receiving is just about perfect.	Strongly Disagree	Disagree	Uncertain	Agree	Strongly Agree
Sometimes doctors make me wonder if their diagnosis is correct.	Strongly Disagree	Disagree	Uncertain	Agree	Strongly Agree
I feel confident that I can get the medical care I need without being set back financially.	Strongly Disagree	Disagree	Uncertain	Agree	Strongly Agree
When I go for medical care, they are careful to check everything when treating and examining me.	Strongly Disagree	Disagree	Uncertain	Agree	Strongly Agree
I have to pay for more of my medical care than I can afford.	Strongly Disagree	Disagree	Uncertain	Agree	Strongly Agree

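### The Aim 3 target (8 points, SD 12) is not tied to the 3-item satisfaction score named as the endpoint, and does not equal the 0.75 SD printed beside it

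*Combined protocol and SAP*

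**What the plan says.** Aim 3 (C.2, Data Analyses) tests this hypothesis: "Survivors in PCI will report greater satisfaction with their cancer care compared to UC participants". The endpoint is named in C.1, Secondary Outcomes, item (b). Satisfaction with care "will be measured with 3 reliable items used by" a team member in earlier work, citing reference 109. The number of response options, the score range and the scoring method are not given.

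The Aim 3 power statement opens with "With 50 Latina survivors per arm we will have 96% power". The effect behind that figure, which the plan calls clinically significant and tests at the 0.05 level, is given as a "difference in satisfaction with care of 8 points (0.75 SD given estimated SD of 12". The citation here is reference 120, which the reference list shows to be a study of doctor-patient communication in adjuvant therapy discussions. It is not the source cited for the three items.

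The interview is in "Appendix D: Draft Baseline Interview". The only satisfaction content there is Section M, Medical Care Experiences: 16 five-point agree/disagree items, given to survivors and caregivers, about "the overall medical care you have received from the doctor you see the most often". No 3-item satisfaction scale is identified in the appendix. The replication plan says of the interview: "We have developed a draft of our baseline assessment measure that includes most (although not all) items we propose to measure".

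**The concern.** A target difference in points, and an SD in points, mean something only on the score that will be analysed. Here the instrument comes from one source and the points from another, and the instrument's scoring is not stated. A reader cannot tell whether 8 points is a small, plausible or impossible difference on the Aim 3 endpoint. If the score turns out to be a plain sum of three ordinary rating items, the stated SD cannot occur on it.

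The trial would then have no usable benchmark for a clinically significant Aim 3 result. With no score defined, the choice of score could also drift until after data collection. Satisfaction with care is in the trial's main research question and has its own aim, hypothesis and power figure, so this deserves tidying even for a secondary outcome.

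**Working it through.** **Inputs.** From C.2, Aim 3: n = 50 per arm, difference 8, SD 12, standardised difference 0.75, power 96%, significance level 0.05 (sidedness not stated). From C.1: three items, format not stated. From Appendix D, Section M: 16 items with five options. Assumptions made here: the number of response points per item, and scoring from 1 upward as a raw sum.

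**1. The plan's own power figure.** For two means, power ≈ Φ(d·√(n/2) − 1.96), with √(50/2) = 5.
- d = 0.75: 0.75 × 5 = 3.75; 3.75 − 1.96 = 1.79; power 96.3% (noncentral t: 96.0%). This reproduces the stated 96%.
- d = 8/12 = 0.667: 0.667 × 5 = 3.33; 3.33 − 1.96 = 1.37; power 91.5% (noncentral t: 91.0%). This does not reproduce it.

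So 96% was computed from 0.75 SD, and 0.75 SD does not follow from 8 points and SD 12. To agree, the difference would have to be 9 points (0.75 × 12), or the SD 10.67 (8/0.75). Keeping 8 points, SD 12 and 96% would need 62 per arm by the normal formula, or 63 by the t.

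A one-sided test at 8/12 gives 95.2% to 95.4%, close to the stated figure. However, the plan states one-sided testing nowhere. The 84% for Aim 1 (6 points, 0.6 SD, 50 per arm) also fits only a two-sided test: 84.4% to 85.1% two-sided, against 90.9% to 91.2% one-sided.

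**2. Can a 3-item score have SD 12?** The SD of a bounded score is at most half its range. A sum of three items with k response points has range 3(k − 1), so its maximum SD is 3(k − 1)/2.

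| Response points per item (assumed) | Width of summed range | Maximum SD |
|---|---|---|
| 4 | 9 | 4.5 |
| 5 | 12 | 6.0 |
| 7 | 18 | 9.0 |
| 8 | 21 | 10.5 |
| 9 | 24 | 12.0 |
| 10 | 27 | 13.5 |

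SD 12 is therefore impossible on a raw sum with up to 8 response points. With 9 or 10 points it would need nearly all answers at the two extremes. On five-point items (3 to 15), 8 points is 8/12 = 67% of the range. The match with 0.667 SD is a coincidence, because the range width and the stated SD are both 12.

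**3. What would make SD 12 possible.**
- Rescaling to 0-100: maximum SD 50. For five-point items, 8 points is then 0.08 × 12 = 0.96 raw points, and SD 12 is 0.12 × 12 = 1.44 raw points.
- A longer scale: a 16-item five-point sum runs from 16 to 80, with maximum SD 32, and 8 points is 8/64 = 12.5% of the range.

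The plan states neither a rescaling nor a longer scale for Aim 3.

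**4. Endpoint against draft interview.** The hypothesis concerns cancer care. Section M asks about overall medical care from the doctor seen most often. It has 16 items, not three, and no text links it to Aim 3.

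**The case against.** The strongest reply is that only one instrument is named, that the interview is openly a draft, and that the power figure rests on a scale-free 0.75 SD. Much of this stands, and it rules out several stronger readings.

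- *Three competing instruments.* A reader might infer this. The 8-point/SD 12 figure is a power assumption, not an instrument, and Section M is never called the Aim 3 measure. The three items may simply not have been added yet. The 15-item provider-communication measure and the adherence items promised in C.1 are also absent from the draft.
- *SD 12 is impossible on the endpoint.* This holds only for a raw sum with usual response formats. The scoring is unstated, and a 0-100 rescaling removes the impossibility.
- *The points belong to another scale.* The documents show only that the citations differ. The scale used in reference 120 cannot be seen here.
- *At follow-up the question covers care received before randomisation.* Appendix D is a baseline form. No follow-up interview is shown, so its recall period is unknown.
- *The trial cannot test satisfaction with cancer care.* The mixed-model comparison of arms works on any continuous score.

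The draft status of Appendix D does not answer the main point. The C.1 and C.2 statements are both main protocol text. They fail to connect whatever the final interview contains, and 8/12 is not 0.75 on any scale.

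**Conclusion.** The point holds as a gap in specification and an inconsistent target, not as a failure of the design. The Aim 3 score is undefined beyond its number of items, and the 8-point/SD 12 target is not tied to it. On a raw sum of three items with up to 8 response points that SD cannot occur; on 1-to-5 items the ceiling is 6.0. This conclusion assumes a raw sum and would not apply to a rescaled score.

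The arithmetic error needs no assumption about the scale: 8/12 is 0.667 SD. At 50 per arm and two-sided 0.05, that gives about 91% power in place of the stated 96%. The loss is modest and leaves the aim well powered for the printed difference. The consequence is that the Aim 3 result has no clear benchmark in points. Because this is a secondary outcome and the repair is simple, it should be corrected, but it does not threaten the trial.

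**What to change.** 1. In C.1, in C.2 Aim 3 and in the final interview, confirm the 3-item cancer-care score as the sole Aim 3 endpoint. State its response format, its range, and whether it is a sum, a mean or a rescaled score.
2. If Section M is kept, label it descriptive only.
3. Replace the 8-point/SD 12 sentence with a target difference and SD on the 3-item score, or give the target in SD units only. Print the power that matches, with 50 per arm and two-sided 0.05 stated explicitly: about 96% at 0.75 SD, or about 91% at 0.667 SD.

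The cost is a few sentences in the protocol and interview, best settled before enrolment in the final protocol, coding instructions and analysis plan that the replication section already promises. The sample size need not change unless the team wants to keep 96% power at 0.667 SD, which would take 62 to 63 analysed survivors per arm. The team will need a defensible SD for the 3-item score; if none is available, the SD-unit version avoids the problem.

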^bCentral American other than Mexican

Ascertainment and Enrollment: Interviews. Eligible Latina survivors and caregivers will be recruited from our four sites or referred by a collaborating hospital or clinic. Contacts at each site will help identify eligible Latina survivors and will mail a study flyer inviting them and a primary caregiver to be involved in an in-depth interview. We will also use in-person recruitment to talk with survivors and caregivers at the four sites (e.g., at the time of patient navigation). If a survivor and/or caregiver is interested, a team member will follow up with further information about the study to determine eligibility and obtain consent from both individuals in the dyad.

Ascertainment, Enrollment and Retention: RCT. With over 2 years of enrollment into the RCT, we anticipate a total of 750 Latina survivor-caregiver dyads identified at the four

sites with a minimum of 300 eligible dyads. We will establish procedures to identify eligible women by having the Project Director/Project Manager (PD/PM) at each site develop an eligibility checklist for their use. The PD at GUMC will coordinate this process across sites to ensure consistency. The PD/PM will check in weekly with the PD at GUMC to provide names of women who provided permission for the team to contact them. We will recruit caregivers through Latina survivors, a strategy that has been very successful at Nueva Vida. We will enroll 125 dyads. We have retained over 80% of Latina survivors in prior work.²⁵ We thus expect to retain 100 survivor-caregiver dyads at 6-months. We will discuss strategies to promote retention through teleconferences and annual meetings. We will customize strategies to each site.

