Randomization. After the baseline, we will randomize participants to PCI or UC via computer by the method of permuted blocks with blocks of size four. We will stratify randomization by location (DC, NY, CA). The GUMC PD will help guide each site PD/PM on accessing/using the web-based randomization database. Randomization is expected to balance key demographic factors such as age, time since diagnosis and survivors' stage of disease between the PCI and UC arms. We will carefully examine these factors in analyses and control any variables as appropriate.

RCT Implementation. Following randomization, survivor-caregiver dyads will begin either the PCI or proceed with UC. PCI sessions will be held at one of the four community partner sites and led by the trained bilingual and bi-cultural interventionists. Interventionists will work with the PD in DC to track intervention delivery process measures and participant attendance. We will use rolling recruitment and begin new groups as we enroll participants. Groups will consist of approximately 10 survivor-caregiver dyads each (n=20 in each PCI wave; n=10 in each PI wave). Groups will be closed such that newly enrolled participants will wait to begin a group until ~10 new dyads are identified.

Post-intervention and 6-month Follow-Up Interviews. Follow-up interviews assess QOL, secondary outcomes, proposed mediating variables (communication self-efficacy, social support, distress), cultural, contextual and dyadic factors (Table 4). We also will assess intervention process. Follow-up interviews will be 25 minutes and administered by telephone and conducted by the bilingual RA using internet-based data entry screens through the PROMIS Assessment Center. Participants will receive \$10 for each completed interview.

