1. RISKS TO THE SUBJECTS

a. Human Subjects Involvement, Characteristics, and Design

For the proposed study, we will recruit participants from local hospitals and community-based organizations including: LatinaSHARE (New York, NY), Nueva Vida Inc. (Washington, DC), Latinas Contra Cancer (New York, NY) Gilda's Club NYC (New York, NY) and St. Luke's-Roosevelt Hospital (New York, NY). We may also receive referrals to the study through existing collaborations of study team members with St. Barnabas Hospital (New York, NY), Doctors Community Hospital (Lanham, MD) and Signature Breast Care (Lanham, MD). The proposed study consists of **refining the intervention** and a **randomized controlled trial**. The study population will be Latina breast cancer survivors and their caregivers. Caregivers will be a primary support person identified by the survivor. We anticipate that 10 patient-caregiver dyads will participate in refining the intervention, and 125 patient-caregiver dyads will participate in the randomized trial (allowing for attrition, we expect a final sample size of 100 dyads). Latina breast cancer survivors will be eligible for this study if they: 1) self-identify as Latina, 2) have been diagnosed with breast cancer, 3) speak English or Spanish, 4) can provide meaningful consent (i.e. men and women with severe cognitive impairment will be excluded), 5) can identify at least one primary, adult caregiver. Caregivers of Latina breast cancer survivors will be eligible if they: 1) are aged 21 to 80 years, 2) speak English or Spanish, 3) can provide meaningful consent (i.e. men and women with severe cognitive impairment will be excluded). Following IRB approval and with a HIPAA waiver, contacts at each community site (LatinaSHARE, Nueva Vida, Latinas Contra Cancer, Gilda's Club NYC) will help identify eligible Latina survivors and will mail a bilingual study invitation letter inviting them and a primary caregiver to be involved in refining the intervention or the randomized controlled trial. Potential participants will be provided with several easy ways to decline the study or opt out of additional contact. For example, study invitation letters will include a pre-stamped decliner postcard and a telephone number to call a study-dedicated line. Those who do not decline within 2 weeks of receipt of the study letter will be contacted via telephone by a member of the study team. During this initial telephone screening call, women will be invited to decline if they are not interested. If they are interested, the research assistant will further explain the study and determine initial eligibility based on self-reported cancer history, age and ethnicity. We will also use in-person recruitment to talk with survivors and caregivers at the four sites. If a survivor and/or caregiver is interested, a study team member will follow up with further information about the study to determine eligibility and obtain consent from both individuals in the dyad. Our community partners at Nueva Vida have had success recruiting caregivers into their program by encouraging the Latina survivors to invite the caregivers into the program. We will use this strategy and others developed by the study team to recruit both survivors and caregivers into the proposed project.

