- 1) **Letter of Intent** – This document indicates the intent of both GUMC and the subcontractor to establish the structural and financial arrangements needed to carry out the proposed work. In addition, this document indicates the subcontractor's agreement to follow GUMC's policies related to disclosure of any potential conflicts of interest specific to this study. Each Letter of Intent has been signed by the authorized officials at each of GUMC and each of the collaborator community organizations.
- 2) **Statement of Work** – This document indicates the scope of work to be carried out by each of the collaborator community organizations. These details include: participating in annual team meetings, conference calls and interventionist training; implementing the patient-caregiver intervention; and reporting and tracking of potential and enrolled participants and the expected number of enrolled participants recruited at each site during each of the study years. The estimates for the number of participants to be enrolled at each site were established through discussion with each of the subcontractors to reflect the realistic capacity to carry out the proposed research within the specific time and fiscal constraints. All four organizations will implement the patient-caregiver intervention and will participate fully in all aspects of the study, including use of a GUMC-central randomization system to randomize participants to either the intervention or usual care. This document was signed and dated by each of the subcontract PIs and [name] from GUMC.
- 3) **Budget and Budget Justification** – As required by both the PCORI submission guidelines and GUMC processes for subcontractors, each subcontract site submitted a detailed budget for each of the years of the proposed study along with an accompanying budget justification. Each site prepared and submitted to GUMC for review their budget and budget justification. As evident from the budget documents submitted from the four organizations, each one identified the administrative and personnel structure and organization that would work best for their individual site.

PRINCIPAL INVESTIGATOR (LAST, FIRST, MIDDLE): [name]

PROJECT PLAN AND TIMELINE

Below is our study timeline, with study tasks, milestones and deliverables and their estimated dates of submission or completion. Deliverables are highlighted in the left-hand column with shading.

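### A single fixed block size of four, with site staff who refer dyads also using the randomisation database, leaves up to a third of allocations foreseeable where staff know the earlier assignments

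*Combined protocol and SAP*

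**What the plan says.** The allocation method is in section C.2, Randomization. After the baseline, "we will randomize participants to PCI or UC via computer by the method of permuted blocks with blocks of size four". The strata are three locations: DC, NY and CA. The same paragraph adds: "The GUMC PD will help guide each site PD/PM on accessing/using the web-based randomization database".

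Other sections show who does what:

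- **Screening.** C.2 (Ascertainment, Enrollment and Retention: RCT) sets up identification of eligible women by "having the Project Director/Project Manager (PD/PM) at each site develop an eligibility checklist for their use". The same role passes names to Georgetown (GUMC) each week.
- **Invitation.** Under Protection of Human Subjects (Risks to the Subjects, part a), contacts at each community site "will help identify eligible Latina survivors and will mail a bilingual study invitation letter inviting them and a primary caregiver". In-person recruitment at the sites is also planned.
- **Delivery.** C.2 (RCT Implementation): "PCI sessions will be held at one of the four community partner sites", in closed groups of about 10 dyads.
- **Systems.** The Statement of Work, under Inter-Organizational Agreement Information, commits all four organisations to "use of a GUMC-central randomization system to randomize participants to either the intervention or usual care". The replication plan adds: "Study team members will use a central study database so that participant tracking is consistent across study sites".
- **Safeguards.** Both members of a dyad finish baseline before randomisation (C.2, Implementation). Participants learn their arm only once written consents are on file (Protection of Human Subjects, section 2a). Blinding is described only for the outcome assessor, as an effort (C.1, Choice of Outcomes).

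No section varies the block size, withholds it from sites, or says what site staff can see of earlier assignments.

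**The concern.** With a known fixed block, anyone who has seen the earlier assignments in a stratum can sometimes deduce the next one. Here the people who could deduce it also influence which dyads come forward. The plan expects at least 300 eligible dyads for 125 places, so there is room for choice. PCI groups start only when about 10 new dyads are available, which gives staff an ordinary, well-meant reason to prefer available and motivated dyads when a PCI place is next.

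Steering of that kind would make the arms differ in prognosis before treatment starts. The primary outcome is self-reported quality of life. The plan's covariate adjustment covers only measured variables, and Table 4 lists no measure of motivation or availability.

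**Working it through.** **Plan's own figures.** The documents give no figure for predictability. The sizes used here do reproduce: 100 / 0.80 = 125 dyads. For 50 per arm, 6 points, SD 10 and two-sided 0.05 (sidedness assumed), power is 84.4% by the noncentral t, against the stated 84%.

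**Step 1: certain places in a 1:1 block of four.** There are six equally likely orders. Two (PPUU, UUPP) fix places 3 and 4. The other four fix only place 4.

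Certain share = (2 × 2 + 4 × 1) / (6 × 4) = 8/24 = 1/3, or 4/3 of a place per block.

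**Step 2: guessing the arm that is behind.** Over the same six orders, with a coin toss at ties, the guess is right 17/24 = 70.8% of the time, against 50% by chance.

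**Step 3: dyads per location (assumption).** Enrolment by location is not given. A 25/25/50 split for DC/CA/NY reproduces every row of the last column of Table 5 to within 1 percentage point. For example, Mexican: 0.25 × 6 + 0.25 × 68 + 0.50 × 27 = 32%, as printed. Central American: 0.25 × 57 + 0.25 × 1 + 0.50 × 5 = 17%, printed as 18%. That gives about 31, 31 and 62 dyads.

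**Step 4: number of certain allocations, allowing for an incomplete last block.**

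- DC or CA: 31 dyads = 7 full blocks plus 3 places. 7 × 4/3 + 1/3 = 9.67, or 31%. The two together give 19.3 of 62.
- NY, every assignment seen: 62 dyads = 15 full blocks plus 2 places. 15 × 4/3 = 20.
- NY, only half of the assignments seen but the place in the block known: 8.3% × 62 = 5.1.

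| Visibility | Certain allocations |
|---|---|
| DC and CA only | about 19 |
| plus NY, half seen | 19.3 + 5.1 = about 24 |
| plus NY, all seen | 19.3 + 20 = about 39; 125/3 = about 42 if every block is complete |

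**Step 5: effect of varying the block size.** This was simulated with 2,000 sequences per setting. The observer knows the set of sizes and every earlier assignment, and updates exactly.

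| Block sizes | Certain, stratum of 31 / 62 | Best guess right, 31 / 62 |
|---|---|---|
| 4 only | 31.3% / 32.3% | 69.9% / 70.4% |
| 4 and 6 | 5.7% / 5.5% | 68.5% / 69.1% |
| 4, 6 and 8 | 2.1% / 2.1% | 67.2% / 67.8% |

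A single larger fixed block does much less for certainty: 25% with blocks of 6 and 20% with blocks of 8. Guessing barely improves because the lagging arm can be followed without knowing where a block ends. In complete blocks, mixing 4, 6 and 8 equally gives (2.833 + 4.1 + 5.329) / 18 = 68.1%, slightly above the 66.6% for a fixed block of 8.

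**The case against.** The strongest reply is that a site controls less than the arithmetic supposes. Names go to GUMC weekly, the study team screens by telephone, a GUMC research assistant interviews survivor and caregiver separately, and only then is the dyad randomised through a central system. A site that picks whom to approach cannot reliably pick the slot that dyad will fill, especially with several dyads pending. This stands. It would be wrong to infer that doing baseline first gives no protection. What it leaves open is steering over whom to put forward when a particular arm is expected, and over when to randomise a dyad that is ready.

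Second, staff sight of assignments is inferred. The plan does not say what the database displays, and does not call the trial open-label. Group attendance shows who is in PCI, but not the order of assignment. This also stands. A reader might infer that a third of all 125 allocations will be foreseen. The documents do not support that: two organisations share the NY stratum, and nothing says that either sees the other's assignments.

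Third, closed groups of about 10 dyads favour tight balance within a location, and the plan will examine and adjust for prognostic factors. The first is a fair reason to keep blocks small. The second helps only for measured variables.

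**Conclusion.** The weakness is real and worth correcting before the list is generated. It is a risk of selection bias; nothing in the documents shows that bias occurred, and the plan's power figure is unaffected.

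The size depends on visibility. About 19 of 62 dyads in DC and CA could be foreseen with certainty if staff there know the block size and every earlier assignment in order, on the assumed 25/25/50 split. About 42 of 125 is the ceiling, reached only if NY staff also see their whole stratum. The one-organisation premise for CA follows the consortium section, which places Latinas Contra Cancer in San Jose; one list under Protection of Human Subjects places it in New York.

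The remedy should not be credited with more than it does. A reader might expect varied blocks to make allocation close to unpredictable. They remove nearly all certainty but leave guessing at about 67-68%.

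**What to change.** In C.2, Randomization, replace the single block size with block sizes that vary at random within location (for example 4, 6 and 8). Have the list generated centrally at GUMC, and keep the sizes out of any document the sites hold. Require that a dyad be irrevocably registered before its assignment is released. State what the database shows site staff of earlier assignments. Central randomisation and completion of both baselines are already in the plan and need no change.

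On the assumed split, certain allocations in DC and CA fall from about 19 to about 1 (2.1% × 62 = 1.3).

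**Cost.** A regenerated list and a short text edit. The largest arm difference within a location rises from 2 dyads to 4, so from 6 to 12 over three locations. If a difference of 12 carried through to the 100 analysed dyads (56 against 44), the standardised difference would be 6 / (10 × √(1/56 + 1/44)) = 2.98 instead of 3.00. Normal-approximation power would be about 84.6% instead of 85.1%, which is negligible. If balance for filling the closed groups matters more, sizes 4 and 6 hold the difference within a location to 3 and still cut certain allocations to about 5.6%.
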